1.3. Study Rationale

There are a range of primary ocular surface disorders that can cause a defect of the corneal epithelium such as chemical injuries, thermal injuries, neurotrophic keratitis, keratoconjunctivitis sicca, cicatricial pemphigoid, Stevens-Johnson syndrome, or toxic epidermal necrolysis (Letko *et al.*, 2001).

The purpose of this study is to investigate the effect of NEXAGON in treating wounds to the eye that have been caused by severe chemical and/or thermal injuries and which have remained unhealed [REDACTED]
[REDACTED] despite conventional medical and surgical standard of care treatment over that period.

NEXAGON, which is a topical gel [REDACTED], has [REDACTED]
[REDACTED]

As detailed in [Section 1.2.2](#), Effect in Humans – Clinical Summary, encouraging clinical results have been shown in eight patients treated with NEXAGON on a compassionate use basis. Each patient had a PED as a result of chemical and/or thermal injuries and re-epithelialization of the cornea could not be achieved by standard of care alone. Details of all eight patients are provided in the latest edition of the Investigator's Brochure for NEXAGON - Ocular Administration [REDACTED]
[REDACTED]

The rationale for this current study is to determine, under a formal clinical protocol, whether NEXAGON is an effective treatment modality for PEDs that have developed as a result of severe chemical and/or thermal injuries, and which are non-responsive [REDACTED] Two dose concentrations of NEXAGON will be assessed against a Vehicle control.

1.4. Dose Concentration, Administration and Regimen Rationale

NEXAGON is formulated with two components, namely the active pharmaceutical ingredient (API), called CODA001 which is an unmodified [REDACTED] oligonucleotide [REDACTED]
[REDACTED]

NEXAGON [REDACTED] have been selected as the two dose concentrations to be used in this study. The comparator will be the Vehicle [REDACTED]
[REDACTED].

The primary endpoint will be corneal epithelial recovery, [REDACTED]
[REDACTED]

Previous dosing experiences of NEXAGON in ocular indications are as follows:

- **Study NEX-OCU-001:** A Phase 1, dose-rising safety study in 26 participants which assessed the safety of [REDACTED] of [REDACTED] of NEXAGON applied to the de-epithelialized eye following photo-refractive keratectomy. There were no side effects or dose-limiting toxicities attributable to any dose of NEXAGON in any of these subjects in this study. Therefore, all four dose concentrations were safe and tolerated when applied to a wounded human eye.
- **Study NTX-OCI-001:** A Phase 2 randomized, prospective, double-masked, vehicle-controlled study to evaluate the safety and efficacy of topical NEXAGON in subjects with ocular surface chemical burns. Subjects were randomized to either NEXAGON ([REDACTED]

[REDACTED] the equivalent volume of NEXAGON Vehicle. Investigational product was given on [REDACTED] in addition to the subjects receiving standard of care. Clinical doses of [REDACTED] was chosen largely based on the previous Phase 1 study and the anticipated effect of standard of care on NEXAGON application. No overt toxicity was seen in NEX-OCU-001 [REDACTED] or in the animal toxicology studies up to 32 mg/mL (3.2%) per eye. The study was closed due to slow enrollment after a total of 34 of 66 subjects were recruited, analysis of the data indicated that further investigation of the effects of NEXAGON in patients with severe ocular burns that are more difficult to heal was warranted in a subsequent trial.

- **Ocular Compassionate Use Cases:** Eight patients with a PED resulting from chemical or thermal injuries have been treated with NEXAGON on a compassionate use basis as re-epithelialization of the cornea could not be achieved by standard of care. The dose concentrations used in the compassionate use settings have included [REDACTED] and whilst some subjects had [REDACTED], others required [REDACTED] applications to achieve re-epithelialization. Total doses administered ranged from [REDACTED] to 8.2 mg (refer to the latest edition of the Investigator's Brochure for Nexagon® – Ocular Administration).

For the first 6 compassionate use cases, NEXAGON was applied by being extruded from a syringe [REDACTED]. However, following Protocol NTX-OCI-001, the two most recent compassionate use patients received NEXAGON on [REDACTED]. Re-epithelialization was achieved in both these later subjects, although the most recent case also underwent bilateral AMT and further applications of NEXAGON to achieve healing.

- **Toxicology:** [REDACTED]

1.4.1. Dose Concentration Selection

Whilst prior ocular use in the compassionate use setting has demonstrated positive activity with dose concentrations [REDACTED] higher dose concentrations have also yielded encouraging results, especially in subjects with very severe ocular injuries. Due to the nature of these severe ocular injuries, it is expected that the increased inflammation and increased tearing in the eye will give a combined dilution effect on the applied topical drug.

[REDACTED]
The lower dose concentration of NEXAGON [REDACTED] provides continuity [REDACTED] used to treat 8 subjects under a compassionate use situation. Efficacy by way of re-epithelialization and preservation of the eyes, was demonstrated in this series of subjects after the PEDs were deemed refractory to standard of care. However, until now the dose concentration of

[REDACTED] has yet to be evaluated formally in a randomized, double-masked, controlled clinical trial setting.

Similarly, a higher dose concentration of NEXAGON [REDACTED] has also been selected for this study. This is because the severity of ocular injuries to be included in the study are associated with increased inflammation and increased tearing. [REDACTED]

[REDACTED] This dose is substantially lower than the dosing administered in toxicology study GLP-2017-0024, where multiple repeat applications of NEXAGON [REDACTED] were applied over [REDACTED] to mechanically wounded and non-wounded rabbit eyes. Study GLP-2017-0024 did not show any signs of toxicity, nor impede corneal re-epithelialization between wounding days.

1.4.2. Dose Administration and Regimen

A single dose administration of investigational product – either NEXAGON [REDACTED] or Vehicle – [REDACTED]

[REDACTED] . [REDACTED]

The dosing schedule for this study [REDACTED]

After randomization, investigational product will be administered [REDACTED]

For Protocol NEX-PED-005, the lowest dose concentration of NEXAGON [REDACTED] will equate to a total daily dose of [REDACTED] per application. This dose lies within the therapeutic window used for previous compassionate use patients and overlaps previous clinical experience. [REDACTED]

The compassionate use series of patients indicated that [REDACTED] may sometimes be required to attain re-epithelialization in the most severe or resistant cases. Therefore, if re-epithelialization has not occurred by [REDACTED] another investigational product application will be permitted. This dosing schedule is based on compassionate use experience and with the expectation that initial healing will likely begin immediately following the [REDACTED] doses. [REDACTED]

However, if by [REDACTED] corneal re-epithelialization has still not occurred, those subjects will receive [REDACTED] salvage dose applications of NEXAGON [REDACTED], irrespective of the investigational product assignment at randomization. The rationale for receiving [REDACTED] is

to enable all unhealed subjects enrolled into the study - particularly those randomized to Vehicle - the opportunity of receiving application(s) of investigational product at the highest dose concentration of NEXAGON available.

2. STUDY OBJECTIVES

The objective of this study is to assess the efficacy and safety of two topical ocular dose concentrations of NEXAGON as a treatment for non-healing corneal PEDs resulting from severe chemical and/or thermal ocular injuries.

3. STUDY ENDPOINTS

Primary Endpoint

- Corneal epithelial recovery, defined as a cornea that re-epithelializes by [REDACTED] of treatment and remains re-epithelialized for at [REDACTED] after initial re-epithelialization was first recorded, as assessed by the Investigator.

Secondary Endpoints

Exploratory Endpoints

Safety

- Incidence of Treatment Emergent Adverse Events.

4. INVESTIGATIONAL PLAN

4.1. Study Description

The purpose of this Phase 2 protocol is to evaluate the efficacy and safety of two topical ocular dose concentrations of NEXAGON in subjects with corneal PEDs arising from severe chemical and/or thermal injuries which are non-responsive to current standard of care.

Enrollment for this study will continue until [REDACTED] complete the study. Up to a maximum [REDACTED] [REDACTED] in total will be randomized. The study is double-masked, and neither the Investigator, subject, nor Sponsor/CRO personnel involved in the day to day protocol activities will know which treatment group has been allocated. Subjects will be randomized to either Group A (NEXAGON [REDACTED]), Group B (NEXAGON [REDACTED]) or Group C (Vehicle).

Potentially eligible subjects will be those who present with a clinically non-infected persistent epithelial defect as a result of a severe chemical and/or thermal injury refractory to standard of care. Clinical signs of the ocular injury include de-epithelialization, conjunctival inflammation (hyperemia), limbal ischemia and corneal edema.

Before entry of a subject into this protocol can be considered, the PED must have been present for a minimum of 14 days, [REDACTED]

As detailed in the study entry criteria, for subjects presenting with bilateral ocular surface damage, only one eye will be eligible to be the 'study eye' [REDACTED]

If the Investigator has any doubts about the eligibility of a subject, he/she will be advised to contact the study Sponsor/Medical Monitor to discuss the case further to determine whether the subject is eligible to participate in this protocol.

All subjects who are considered for study inclusion will first have the study explained to them in full. If they are willing to participate, written informed consent will be obtained before any study-related procedures are performed. ONLY subjects that meet all of the inclusion criteria and have no exclusion criteria will be eligible for randomization to double-masked investigational product.

[REDACTED]
[REDACTED] No topical ocular drops or ointments are permitted within [REDACTED] prior to investigational product application or [REDACTED] after.

The study will comprise of 2 periods:

- [REDACTED] **masked Treatment Period**, where investigational product will be applied [REDACTED]. Each subject will attend [REDACTED] assessment visits until corneal re-epithelialization occurs. If by [REDACTED] re-epithelialization has not occurred, the subject will enter the open-label section of the study and receive [REDACTED] salvage dose applications of NEXAGON [REDACTED]
- **Post-healing Follow-up Period**, which will commence as soon as re-epithelialization occurs in the Treatment Period in order to assess durability of the healed cornea [REDACTED] later; the masking will remain during this period.

For all subjects, the first investigational product application will occur following randomization on [REDACTED]

Refer to [Section 7](#) and the Pharmacy Manual for instructions on investigational product administration.

During the Treatment Period, masked investigational product will initially be administered [REDACTED]

If re-epithelialization of the defect has NOT occurred by [REDACTED] another single application of masked investigational product will be administered.

If re-epithelialization occurs [REDACTED] during the masked Treatment Period, subjects will enter a [REDACTED] Follow-up Period to assess durability of the corneal epithelium.

However, if by [REDACTED] of the masked Treatment Period, the cornea has still not fully re-epithelialized, then subjects will receive a salvage treatment dose of NEXAGON [REDACTED]

[REDACTED] If re-epithelialization has not been achieved after [REDACTED] a second salvage dose of NEXAGON [REDACTED] Final assessment of healing for these subjects will be conducted on [REDACTED]

If re-epithelialization has not occurred by [REDACTED] the subject will exit the study.

Once re-epithelialization has occurred, [REDACTED], the subject will enter the Post-healing Follow-up Period and [REDACTED]

[REDACTED]. Subjects will be assessed again [REDACTED] following initial re-epithelialization to confirm durability of the epithelium. The subject will then exit the study having completed all visits.

If the healed epithelium is not sustained within the Post-healing Follow-up Period, the subject will exit and receive the salvage dose(s) as part of the open-label section of the study. If a re-epithelialized cornea develops following the salvage dose application(s), these subjects will also be followed for [REDACTED] to assess durability of healing.

[REDACTED]

At each study visit, following randomization until the end of the study, the subject will undergo assessments as detailed in **Table 1 (Schedule of Assessments)**. Assessments will be performed by a designee at the study site who is masked to the allocated investigational product [REDACTED]

[REDACTED]

[REDACTED] The occurrence of any Treatment Emergent Adverse Events will also be assessed at each study visit, and up to [REDACTED] following the final application of investigational product.

Please refer to Table 1 (Schedule of Assessments) and to Section 6 for full details of study assessments and procedures required at each visit. Figure 2 (Study Flow Diagram) shows the schedule of visits and dosing days.

4.1.1. Study Visit Windows

Subject's visit dates can be booked within the windows detailed in **Table 1: Schedule of Assessments**. Ensure that when determining the visit dates that these are done with reference to the Day 1 visit date of the Treatment Period and not the subject's previous visit. Visits that are not able to be completed within the windows specified in this protocol must be recorded as protocol deviations.

Note: Day 1 corresponds to the day of randomization, Day 0 is not utilized in this study design.

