APPENDIX 9: [REDACTED]	
REFERENCES	76

LIST OF TABLES

Table 1: Schedule of Assessments.....	24
---------------------------------------	----

LIST OF FIGURES

Figure 1: Dose Regimen	23
Figure 2: Study Flow Diagram - Visit Schedule and Dosing Days	27

PROTOCOL SYNOPSIS

Title	A Phase 2, randomized, prospective, double-masked, vehicle-controlled study to assess the efficacy and safety of Nexagon® (NEXAGON) applied topically in subjects with corneal persistent epithelial defects (PED) resulting from severe ocular chemical and/or thermal injuries.
Study Population	This protocol will enroll up to a maximum of [REDACTED] subjects. A total of [REDACTED] subjects are required to complete this study. All eligible subjects will present with a non-infected, corneal PED as a result of a chemical and/or thermal ocular injury which is refractory to current standard of care for at least 14 days.
Study Objective	The objective of this protocol is to assess the efficacy and safety of two topical ocular dose concentrations of NEXAGON as treatment of non-healing corneal PEDs resulting from severe chemical and/or thermal ocular injuries.
Endpoints	
Primary Endpoint:
 
• Corneal epithelial recovery, defined as a cornea that re-epithelializes by [REDACTED] of treatment and remains re-epithelialized for at least [REDACTED] after initial re-epithelialization was first recorded, as assessed by the Investigator. 
Secondary Endpoints:
 
• [REDACTED]• [REDACTED]• [REDACTED]• [REDACTED] 
Exploratory Endpoints:
 
• [REDACTED]• [REDACTED]• [REDACTED]• [REDACTED] 
Safety:
 
• Incidence of Treatment Emergent Adverse Events.

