	
Refer to Table 1: Schedule of Assessments for details of the visit schedule and the procedures to be conducted at each study visit.

Investigational Product Administration for Randomized Subjects	
Each investigational product dose application [REDACTED]
 
[REDACTED]
 
No topical ocular standard of care treatment will be permitted before or [REDACTED] following investigational product administration.
 
[REDACTED]
 
Three treatment arms will be evaluated in this study. Randomization will be in a [REDACTED] ratio:
 
• GROUP A – NEXAGON [REDACTED]• GROUP B – NEXAGON [REDACTED]• GROUP C – Vehicle 
There will be a single application of investigational product [REDACTED] [REDACTED]. A potential additional application of investigational product will be scheduled [REDACTED] if re-epithelialization has not occurred.
 
If re-epithelialization of the study eye has still not occurred at the end of the [REDACTED] masked Treatment Period, or following initial re-epithelialization durability is not maintained, subjects will receive [REDACTED] salvage dose applications of - NEXAGON [REDACTED] in the open-label section of the study

Study Description	
Potentially eligible subjects will be those who present with a clinically non-infected PED as a result of a severe chemical and/or thermal injury refractory to standard of care. Clinical signs of the ocular injury include de-epithelialization, conjunctival inflammation (hyperemia), limbal ischemia and corneal edema.
 
Before the entry of a subject can be considered, the PED must have been present for at least 14 days, [REDACTED]
 
[REDACTED]
 
Subject consent to participate in the study must be obtained by the Principal Investigator or suitably qualified designee before any protocol-specific procedures are undertaken. Eligibility assessments and baseline evaluations will be performed [REDACTED]
 
[REDACTED]

The first investigational product application will occur following randomization [REDACTED]

[REDACTED] The eye will then be covered with a double eye pad and taped shut for approximately [REDACTED].

Each subject will attend twice-weekly assessment visits until corneal re-epithelialization occurs.

If re-epithelialization of the defect has NOT occurred by [REDACTED] of the masked Treatment Period, another single application of masked investigational product will be administered.

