**Post-healing Follow-up Period (Masked)**

During the [REDACTED] Post-healing Follow-up Period subjects will be assessed [REDACTED] following initial re-epithelialization to confirm durability of the epithelium.

- If the healed epithelium is sustained within the Post-healing Follow Period (durable), the subject will then exit the study having completed all visits.
- [REDACTED]
- [REDACTED]
- [REDACTED]

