#### **13. Efficacy Analyses – Masked Portion of Study**

##### **13.1 Primary Efficacy Outcome Analysis**

The primary efficacy outcome will be the comparison of each dose of NEXAGON to Vehicle for the proportion of subjects with corneal epithelial recovery, defined as a cornea that re-epithelializes [REDACTED] of treatment and remains re-epithelialized [REDACTED] after initial re-epithelialization was first recorded (during the masked treatment portion of the study and assessed by the

Investigator). Subjects who discontinue the study early, or who have missing data resulting in the inability to conclude corneal epithelial recovery, will be considered as not having corneal epithelial recovery (missing data imputed as failure).

The number and proportion of subjects with corneal epithelial recovery will be summarized by treatment group and tested between treatment groups [REDACTED]

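### Does dating visits from Day 1 in Protocol 4.1.1 break a durability interval that runs from the recorded healing date?

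*Protocol*

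**What the plan says.** Protocol 4.1.1 sends sites to Table 1 for the visit windows and gives one rule for dating visits: "Ensure that when determining the visit dates that these are done with reference to the Day 1 visit date of the Treatment Period", rather than from the visit before. It adds that Day 1 is the day of randomization and that a visit outside its window is a protocol deviation. Section 4.1 ties the content of visits to Table 1 throughout: "At each study visit, following randomization until the end of the study, the subject will undergo assessments as detailed in" that table.

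The endpoint uses a subject-specific start. In the synopsis the cornea re-epithelializes "and remains re-epithelialized for at least" a redacted length of time. Protocol section 3 counts that time from "after initial re-epithelialization was first recorded, as assessed by the Investigator". Healing is looked for often: "Each subject will attend twice-weekly assessment visits until corneal re-epithelialization occurs" (synopsis, Study Description).

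Two passages date the follow-up itself. Protocol 4.1 describes the Post-healing Follow-up Period as one "which will commence as soon as re-epithelialization occurs in the Treatment Period in order to assess durability of the healed cornea". SAP 3.1 has subjects assessed at a redacted time "following initial re-epithelialization to confirm durability of the epithelium". For salvage subjects, the synopsis starts follow-up at the first open-label application.

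SAP 3.2 lists two window tables: 1a for subjects who stay for the maximum duration, and 1b arranged by period of the study. It repeats the Day 1 convention and the deviation rule, but not the instruction on how to date visits. SAP 13.1 counts as failures subjects who leave early and those with "missing data resulting in the inability to conclude corneal epithelial recovery, will be considered as not having corneal epithelial recovery".

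**The concern.** The dating rule is general and the endpoint is not. For a healed subject, the visit at which healing was recorded is itself an earlier visit. Timing the durability visit from it therefore uses the kind of anchor that 4.1.1 rules out, and a site cannot obey both instructions to the letter.

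If a site kept to Day 1, any shift of the healing visit within its window would add to the shift of the durability visit within its own. The observed interval could then be shorter than the required minimum. Such a subject might be judged inconclusive and counted as a failure. Only healed subjects can lose the endpoint this way, so an equal loss share s in every arm would shrink each comparison with Vehicle by the factor (1 − s): p₁(1 − s) − p₀(1 − s) = (1 − s)(p₁ − p₀). If short intervals were accepted as recovery instead, recovery would be credited on less follow-up than the definition asks for. Either way, this is the timing of the primary endpoint, so it deserves a check.

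**Working it through.** **Which anchor does each passage give?**

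| Place | Visits covered | Anchor |
|---|---|---|
| Protocol 4.1.1 | Visits booked under Table 1, no exception named | Day 1 |
| Protocol section 3; SAP 2.1 and 13.1 | Durability part of the endpoint | First recorded healing |
| Protocol 4.1; SAP 3.1 | Durability assessment | Initial re-epithelialization |
| Synopsis, Study Periods | Open-label follow-up | First salvage application |
| Protocol Table 1; SAP Tables 1a, 1b | Windows | Redacted |

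The general rule stands alone, and every passage about the post-healing period names the healing date. A pure Day 1 calendar cannot be applied to a period that starts on a different day for each subject. To book the durability visit at all, a site must first ask when healing was recorded. For the frequent visits before healing, the Day 1 rule has an obvious purpose: it stops small delays from accumulating from visit to visit.

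**How far could a literal reading move the interval?** The plan shows no interval or window, so there is no figure to reproduce. Assume a durability interval F = 28 days and visit shifts of up to w = 1, 2 or 3 days, all days in a window being equally likely and independent. Let e₁ be the shift of the healing visit and e₂ that of the durability visit.

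- Day 1 anchor: interval = F + e₂ − e₁, which is short when e₂ < e₁.
- Healing anchor: interval = F + e₂, which is short when e₂ < 0.

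*Windows of ±w on both visits.* Day 1 range F ± 2w; healing range F ± w.

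| w | Day 1 anchor, days | Short | Healing anchor, days | Short |
|---|---|---|---|---|
| 1 | 26–30 | 3/9 = 33% | 27–29 | 1/3 = 33% |
| 2 | 24–32 | 10/25 = 40% | 26–30 | 2/5 = 40% |
| 3 | 22–34 | 21/49 = 43% | 25–31 | 3/7 = 43% |

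The shares agree for every w. With the Day 1 anchor there are w(2w + 1) short pairs out of (2w + 1)², which reduces to w/(2w + 1), the healing-anchor share. Changing the anchor limits the shortfall to w days instead of 2w, but makes it no less frequent.

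*Durability window that cannot open early (e₂ from 0 to w).*

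| w | Day 1 anchor, days | Short | Healing anchor, days | Short |
|---|---|---|---|---|
| 1 | 27–30 | 1/6 = 17% | 28–29 | 0 |
| 2 | 26–32 | 3/15 = 20% | 28–30 | 0 |
| 3 | 25–34 | 6/28 = 21% | 28–31 | 0 |

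Here the anchor does matter. But this case needs a schedule that protects the minimum interval with a one-sided window and yet counts that window from Day 1. No visible text describes such a schedule. The shares do not depend on F.

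**Would a short interval be scored as failure?** The visible rule in SAP 13.1 covers early discontinuation and missing data that prevent a conclusion. A visit made inside its permitted window is not missing. SAP 8.2, on missing or inconclusive data, is redacted.

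**The case for a change.** The best case for a change is that the contradiction needs no redacted text. Section 4.1.1 is fully legible, it is the section a site uses to book visits, and it rejects the earlier visit as an anchor. If Table 1 counts from healing, 4.1.1 is at odds with the table it cites; if Table 1 counts from Day 1, the schedule does not track the endpoint. The endpoint sets a minimum interval, deviations are graded as major or minor before analysis, and the repair would be one or two sentences.

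The wording point stands: 4.1.1 should not be read as covering post-healing or open-label visits, and it does not say so. The step to a wrong interval does not stand. Protocol 4.1 and SAP 3.1 give the specific instruction, and a site following it gets the intended timing. The window table arranged by study period in SAP 3.2 suggests that post-healing visits have their own scheme, although its content is withheld. The sentence in 4.1 that applies Table 1 to the end of the study concerns which assessments are done, not how visits are dated. The shortfalls of 17% to 21% arise only under the one-sided schedule described above. With symmetric windows, most of the worry is about a window that opens early, and nothing visible shows that it does. The open-label anchor lies outside the primary endpoint, which is confined to the masked portion.

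**Conclusion.** No change to the plan follows. Section 4.1.1 states a general booking rule without its obvious exception, and the specific passages supply that exception. This is a gap in wording that sites and analysts fill sensibly. At most, under the assumed ±w windows on both visits, a literal reading adds w days to the possible spread on each side, which is 1 to 3 days in the cases shown, and leaves the frequency of short intervals unchanged. Nothing visible favours one arm. The same visit rules apply to all three groups, and masking is kept through the post-healing period.

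The conclusion rests on sites following the healing-based instruction in section 4.1, and on the redacted tables not contradicting it. The 28 days, the windows and the equally likely visit days are assumptions for illustration. If Table 1 or SAP Table 1b in fact dated the durability visit from Day 1, the point would have to be reconsidered, but the public documents give no sign of that.
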